9.1.2. Interim Analyses for Futility

9.1.2.1. Simon 2-Stage Futility Rules

An interim analysis of efficacy will be conducted in Phase 2 by applying the Simon 2-stage design for each tumor within a given treatment group. During Stage 1, n_1 evaluable subjects treated at the recommended dose and schedule will be enrolled, and if r_1 or fewer responses are observed by the Week 16 assessment, then the cohort will be discontinued. To be counted as evaluable for the calculation in Stage 1, subjects must have discontinued from the study, reached the Week 16 assessment, or had at least 2 scans. As discussed in Section 3.2, the Simon 2-stage designs conducted for each tumor type within each treatment group have design parameters that are determined by historical response rates and will have different sample sizes and futility results depending on the historical response rate. The probability of early termination for Stage 1 in Treatment Groups F, G, and H is summarized in [Table 11](#).

Table 11: Probability of Early Termination for Simon 2-Stage Design in Phase 2 in Treatment Groups F, G, and H

Cohort (Tumor Type)	p_0	p_1	Probability of Early Termination	
			Under H_0	Under H_A
RCC	25%	40%	0.6736	0.0940
Urothelial	20%	35%	0.7134	0.1148
Relapsed to anti-PD-1/L1	10%	25%	0.6769	0.0913

9.2. Data Cutoff for Interim Analysis

As discussed in Section 9.1.1, the DMC will meet every 6 months to review safety analyses. All efficacy and safety analyses will use a clinical data cutoff of 3 weeks before execution of the planned safety or interim analysis. This period will help ensure accuracy of the interim data by providing the sponsor time to perform data review, issue queries regarding data quality issues to sites, and to resolve such queries.

10. CHANGES AND MODIFICATIONS TO THE ANALYSIS PLAN

All versions of the SAP are listed in [Table 14](#).

Table 14: Statistical Analysis Plan Versions

SAP Version	Date
Original	06 FEB 2018

10.1. Changes to Protocol-Defined Analyses

Not applicable.

10.2. Changes to the Statistical Analysis Plan

Not applicable.

APPENDIX A. PLANNED TABLES AND FIGURES

This appendix provides a list of the planned tables and figures for the CSR. Standard tables will follow the conventions in the Standard Safety Tables initial version. Shells are provided for nonstandard tables in a separate document. In-text tables are identical in structure and content as appendix tables, but follow a Rich Text Format.

The list of tables, figures, and the shells are to be used as guideline. Modifications of the list or shells that do not otherwise affect the nature of the analysis will not warrant an amendment to the SAP.

Tables

Table No.	Title	Population	Standard	In-Text
Baseline and Demographic Characteristics				
1.1 Disposition				
1.1.1.1	Analysis Populations	Phase 1 FAS Population	X	X
1.1.1.2	Analysis Populations	Phase 2 FAS Population	X	X
1.1.2.1	Summary of Subject Disposition	Phase 1 FAS Population	X	X
1.1.2.2	Summary of Subject Disposition	Phase 2 FAS Population	X	X
1.1.2.3	Summary of Subject Disposition	FAS Population	X	
1.1.3	Summary of Number of Subjects Enrolled by Country and Site	FAS Population	X	
1.2 Demography				
1.2.1	Summary of Demographics	Phase 1 FAS Population	X	X
1.2.2	Summary of Demographics – by Tumor Type	Phase 2 FAS Population	X	X
1.3 Baseline Characteristics				
1.3.1.1	Summary of Baseline Disease Characteristics and Disease History for Phase 1 Solid Tumor Types	Phase 1 FAS Population	X	
1.3.1.2.1	Summary of Baseline Disease Characteristics and Disease History for Phase 2 Solid Tumor Types	Phase 2 FAS Population	X	
1.3.1.2.2	Summary of Baseline Disease Characteristics and Disease History	RCC Phase 2 FAS Population	X	

Table No.	Title	Population	Standard	In-Text
1.3.1.2.3	Summary of Baseline Disease Characteristics and Disease History	Urothelial Phase 2 FAS Population	X	
1.3.1.2.4	Summary of Baseline Disease Characteristics and Disease History	Relapsed PD-1 Phase 2 FAS Population	X	
1.4 Prior Medication and Concomitant Medication				
1.4.1.1	Summary of Prior Systemic Therapy	Phase 1 FAS Population		
1.4.1.2	Summary of Prior Systemic Therapy – by Tumor Type	Phase 2 FAS Population		
1.4.2.1	Summary of Prior Medications	Phase 1 FAS Population	X	
1.4.2.2	Summary of Prior Medications – by Tumor Type	Phase 2 FAS Population	X	
1.4.3	Summary of Prior Radiation – by Tumor Type	Phase 2 FAS Population		
1.4.4	Summary of Prior Surgery – by Tumor Type	Phase 2 FAS Population		
1.4.5.1	Summary of Concomitant Medications	Phase 1 FAS Population	X	
1.4.5.2	Summary of Concomitant Medications – by Tumor Type	Phase 2 FAS Population	X	
1.5 Others				
1.5.1	Summary of General Medical History	Phase 1 FAS Population	X	
1.5.2	Summary of General Medical History – by Tumor Type	Phase 2 FAS Population	X	
1.5.3	Summary of Protocol Deviations	FAS Population		X

Table No.	Title	Population	Standard	In-Text
2.1 Efficacy				
2.1.1.1	Summary of Confirmed Best Response, Duration of Response, and Duration of Disease Control Under RECIST v1.1 – by Treatment Group and Dose	Phase 1 Response Evaluable Population		X
2.1.1.2	Summary of Unconfirmed Best Response, Duration of Response, and Duration of Disease Control Under RECIST v1.1 – by Treatment Group and Dose	Phase 1 Response Evaluable Population		X
2.1.2.1	Summary of Confirmed Best Response, Duration of Response, and Duration of Disease Control Under RECIST v1.1 – by Treatment Group and Dose	Phase 2 Response Evaluable Population		X
2.1.2.2	Summary of Unconfirmed Best Response, Duration of Response, and Duration of Disease Control Under RECIST – by Treatment Group and Dose	Phase 2 Response Evaluable Population		X
2.1.3.1	Summary of Confirmed Best Response, Duration of Response, and Duration of Disease Control under mRECIST – by Treatment Group and Tumor Type	Phase 2 Response Evaluable Population		X
2.1.3.2	Summary of Unconfirmed Best Response, Duration of Response, and Duration of Disease Control Under mRECIST – by Treatment Group and Tumor Type	Phase 2 Response Evaluable Population		X
2.1.4.1	Summary of Progression-Free Survival Under RECIST v1.1	Phase 1 FAS Population		X
2.1.4.2	Summary of Progression-Free Survival Under RECIST v1.1 – by Tumor Type	Phase 2 FAS Population		X
2.1.5.1	Summary of Progression-Free Survival Under mRECIST	Phase 1 FAS Population		X
2.1.5.2	Summary of Progression-Free Survival under mRECIST – by Tumor Type	Phase 2 FAS Population		X
2.1.6.1	Summary of Overall Survival	Phase 1 FAS Population		X
2.1.6.2	Summary of Overall Survival – by Tumor Type	Phase 2 FAS Population		X

Table No.	Title	Population	Standard	In-Text
Safety				
3.1 Dose Exposure				
3.1.1.1	Summary of INCAGN01949 Drug Exposure – by Treatment Group and Dose	Phase 1 FAS Population	X	X
3.1.1.2	Summary of INCAGN01949 Drug Exposure – by Treatment Group and Tumor Type	Phase 2 FAS Population	X	X
3.1.2.1	Summary of Nivolumab Drug Exposure – by Treatment Group and Dose	Phase 1 Nivolumab FAS Population	X	X
3.1.2.2	Summary of Nivolumab Drug Exposure – by Treatment Group and Tumor Type	Phase 2 Nivolumab FAS Population	X	X
3.1.3.1	Summary of Ipilimumab Drug Exposure – by Treatment Group and Dose	Phase 1 Ipilimumab FAS Population	X	X
3.1.3.2	Summary of Ipilimumab Drug Exposure – by Treatment Group and Tumor Type	Phase 2 Ipilimumab FAS Population	X	X
3.1.4.1	Summary of INCAGN01949 Drug Exposure by Visit – by Treatment Group and Dose	Phase 1 FAS Population		
3.1.4.2	Summary of INCAGN01949 Drug Exposure by Visit – by Treatment Group and Tumor Type	Phase 2 FAS Population		
3.1.5.1	Summary of Nivolumab Drug Exposure by Visit – by Treatment Group and Dose	Phase 1 Nivolumab FAS Population		
3.1.5.2	Summary of Nivolumab Drug Exposure by Visit – by Treatment Group and Tumor Type	Phase 2 Nivolumab FAS Population		

Table No.	Title	Population	Standard	In-Text
3.1.6.1	Summary of Ipilimumab Drug Exposure by Visit – by Treatment Group and Dose	Phase 1 Ipilimumab FAS Population		
3.1.6.2	Summary of Ipilimumab Drug Exposure by Visit – by Treatment Group and Tumor Type	Phase 2 Ipilimumab FAS Population		
3.2 Adverse Events				
3.2.1.1	Overall Summary of Treatment-Emergent Adverse Events – by Treatment Group and Dose	Phase 1 FAS Population	X	X
3.2.1.2	Overall Summary of Treatment-Emergent Adverse Events – by Treatment Group and Tumor Type	Phase 2 FAS Population	X	X
3.2.2.1	Summary of Treatment-Emergent Adverse Events by MedDRA System Organ Class and Preferred Term – by Treatment Group and Dose	Phase 1 FAS Population	X	
3.2.3.1	Summary of Treatment-Emergent Adverse Events by MedDRA System Organ Class and Preferred Term – by Treatment Group and Tumor Type	Phase 2 FAS Population	X	
3.2.4.1	Summary of Treatment-Emergent Adverse Events by MedDRA Preferred Term in Decreasing Order of Frequency – by Treatment Group and Dose	Phase 1 FAS Population	X	X
3.2.4.2	Summary of Treatment-Emergent Adverse Events by MedDRA Preferred Term in Decreasing Order of Frequency – by Treatment Group and Tumor Type	Phase 2 FAS Population	X	X
3.2.5.1	Summary of Treatment-Emergent Adverse Events by MedDRA System Organ Class, Preferred Term, and Maximum Severity – by Treatment Group and Dose	Phase 1 FAS Population	X	
3.2.5.2	Summary of Treatment-Emergent Adverse Events by MedDRA System Organ Class, Preferred Term, and Maximum Severity – by Treatment Group and Tumor Type	Phase 2 FAS Population	X	
3.2.6.1	Summary of Grade 3 or Higher Treatment-Emergent Adverse Events by MedDRA System Organ Class and Preferred Term – by Treatment Group and Dose	Phase 1 FAS Population	X	X
3.2.6.2	Summary of Grade 3 or Higher Treatment-Emergent Adverse Events by MedDRA System Organ Class and Preferred Term – by Treatment Group and Tumor Type	Phase 2 FAS Population	X	X
3.2.7.1	Summary of Any INCAGN01949 Treatment-Related Adverse Events by MedDRA System Organ Class and Preferred Term – by Treatment Group and Dose	Phase 1 FAS Population	X	X
3.2.7.2	Summary of Any INCAGN01949 Treatment-Related Adverse Events by MedDRA System Organ Class and Preferred Term – by Treatment Group and Tumor Type	Phase 2 FAS Population	X	X
3.2.8.1	Summary of Any Nivolumab Treatment-Related Adverse Events by MedDRA System Organ Class and Preferred Term – by Treatment Group and Dose	Phase 1 Nivolumab FAS Population	X	X

Table No.	Title	Population	Standard	In-Text
3.2.8.2	Summary of Any Nivolumab Treatment-Related Adverse Events by MedDRA System Organ Class and Preferred Term – by Treatment Group and Tumor Type	Phase 2 Nivolumab FAS Population	X	X
3.2.9.1	Summary of Any Ipilimumab Treatment-Related Adverse Events by MedDRA System Organ Class and Preferred Term – by Treatment Group and Dose	Phase 1 Ipilimumab FAS Population	X	X
3.2.9.2	Summary of Any Ipilimumab Treatment-Related Adverse Events by MedDRA System Organ Class and Preferred Term – by Treatment Group and Tumor Type	Phase 2 Ipilimumab FAS Population	X	X
3.2.10.1	Summary of Any Grade 3 or Higher INCAGN01949 Treatment-Related Adverse Events by MedDRA Preferred Term in Order of Decreasing Frequency – by Treatment Group and Dose	Phase 1 FAS Population	X	
3.2.10.2	Summary of Any Grade 3 or Higher INCAGN01949 Treatment-Related Adverse Events by MedDRA Preferred Term in Order of Decreasing Frequency – by Treatment Group and Tumor Type	Phase 2 FAS Population	X	
3.2.11.1	Summary of Any Grade 3 or Higher Nivolumab Treatment-Related Adverse Events by MedDRA Preferred Term in Order of Decreasing Frequency – by Treatment Group and Dose	Phase 1 Nivolumab FAS Population	X	
3.2.11.2	Summary of Any Grade 3 or Higher Nivolumab Treatment-Related Adverse Events by MedDRA Preferred Term in Order of Decreasing Frequency – by Treatment Group and Tumor Type	Phase 2 Nivolumab FAS Population	X	
3.2.12.1	Summary of Any Grade 3 or Higher Ipilimumab Treatment-Related Adverse Events by MedDRA Preferred Term in Order of Decreasing Frequency – by Treatment Group and Dose	Phase 1 Ipilimumab FAS Population	X	
3.2.12.2	Summary of Any Grade 3 or Higher Ipilimumab Treatment-Related Adverse Events by MedDRA Preferred Term in Order of Decreasing Frequency – by Treatment Group and Tumor Type	Phase 2 Ipilimumab FAS Population	X	
3.2.13.1	Summary of Any INCAGN01949 Treatment-Related Adverse Events With a Fatal Outcome by MedDRA System Organ Class and Preferred Term – by Treatment Group and Dose	Phase 1 FAS Population	X	
3.2.13.2	Summary of Any INCAGN01949 Treatment-Related Adverse Events With a Fatal Outcome by MedDRA System Organ Class and Preferred Term – by Treatment Group and Tumor Type	Phase 2 FAS Population	X	
3.2.14.1	Summary of Any Nivolumab Treatment-Related Adverse Events With a Fatal Outcome by MedDRA System Organ Class and Preferred Term – by Treatment Group and Dose	Phase 1 Nivolumab FAS Population	X	
3.2.14.2	Summary of Any Nivolumab Treatment-Related Adverse Events With a Fatal Outcome by MedDRA System Organ Class and Preferred Term – by Treatment Group and Tumor Type	Phase 2 Nivolumab FAS Population	X	

Table No.	Title	Population	Standard	In-Text
3.2.15.1	Summary of Any Ipilimumab Treatment-Related Adverse Events With a Fatal Outcome by MedDRA System Organ Class and Preferred Term- by Treatment Group and Dose	Phase 1 Ipilimumab FAS Population	X	
3.2.15.2	Summary of Any Ipilimumab Treatment-Related Adverse Events With a Fatal Outcome by MedDRA System Organ Class and Preferred Term – by Treatment Group and Tumor Type	Phase 2 Ipilimumab FAS Population	X	
3.2.16.1	Summary of Serious Treatment-Emergent Adverse Events by MedDRA System Organ Class and Preferred Term – by Treatment Group and Dose	Phase 1 FAS Population	X	
3.2.16.2	Summary of Serious Treatment-Emergent Adverse Events by MedDRA System Organ Class and Preferred Term – by Treatment Group and Tumor Type	Phase 2 FAS Population	X	
3.2.17.1	Summary of Serious Treatment-Emergent Adverse Events by MedDRA Preferred Term in Decreasing Order of Frequency – by Treatment Group and Dose	Phase 1 FAS Population		X
3.2.17.2	Summary of Serious Treatment-Emergent Adverse Events by MedDRA Preferred Term in Decreasing Order of Frequency – by Treatment Group and Tumor Type	Phase 2 FAS Population		X
3.2.18.1	Summary of Non-Serious Treatment-Emergent Adverse Events by MedDRA System Organ Class and Preferred Term – by Treatment Group and Dose	Phase 1 FAS Population	X	
3.2.18.2	Summary of Non-Serious Treatment-Emergent Adverse Events by MedDRA System Organ Class and Preferred Term – by Treatment Group and Tumor Type	Phase 2 FAS Population	X	
3.2.19.1	Summary of Treatment-Related Serious Adverse Events by MedDRA System Organ Class and Preferred Term – by Treatment Group and Dose	Phase 1 FAS Population	X	
3.2.19.2	Summary of Treatment-Related Serious Adverse Events by MedDRA System Organ Class and Preferred Term – by Treatment Group and Tumor Type	Phase 2 FAS Population	X	
3.2.20.1	Summary of Treatment-Emergent Adverse Events Leading to INCAGN01949 Dose Reduction by MedDRA System Organ Class and Preferred Term – by Treatment Group and Dose	Phase 1 FAS Population	X	
3.2.20.2	Summary of Treatment-Emergent Adverse Events Leading to INCAGN01949 Dose Reduction by MedDRA System Organ Class and Preferred Term – by Treatment Group and Tumor Type	Phase 2 FAS Population	X	
3.2.21.1	Summary of Treatment-Emergent Adverse Events Leading to INCAGN01949 Dose Interruption by MedDRA System Organ Class and Preferred Term – by Treatment Group and Dose	Phase 1 FAS Population		
3.2.21.2	Summary of Treatment-Emergent Adverse Events Leading to INCAGN01949 Dose Interruption by MedDRA System Organ Class and Preferred Term – by Treatment Group and Tumor Type	Phase 2 FAS Population		
3.2.22.1	Summary of Treatment-Emergent Adverse Events Leading to Nivolumab Dose Interruption by MedDRA System Organ Class and Preferred Term – by Treatment Group and Dose	Phase 1 FAS Population		

Table No.	Title	Population	Standard	In-Text
3.2.22.2	Summary of Treatment-Emergent Adverse Events Leading to Nivolumab Dose Interruption by MedDRA System Organ Class and Preferred Term – by Treatment Group and Tumor Type	Phase 2 FAS Population		
3.2.23.1	Summary of Treatment-Emergent Adverse Events Leading to Ipilimumab Dose Interruption by MedDRA System Organ Class and Preferred Term – by Treatment Group and Dose	Phase 1 FAS Population		
3.2.23.2	Summary of Treatment-Emergent Adverse Events Leading to Ipilimumab Dose Interruption by MedDRA System Organ Class and Preferred Term – by Treatment Group and Tumor Type	Phase 2 FAS Population		
3.2.24.1	Summary of Treatment-Emergent Adverse Events Leading to Discontinuation of INCAGN01949 by MedDRA System Organ Class and Preferred Term – by Treatment Group and Dose	Phase 1 FAS Population	X	
3.2.24.2	Summary of Treatment-Emergent Adverse Events Leading to Discontinuation of INCAGN01949 by MedDRA System Organ Class and Preferred Term – by Treatment Group and Tumor Type	Phase 2 FAS Population	X	
3.2.25.1	Summary of Treatment-Emergent Immune-Related Adverse Events (Investigator Identified) by MedDRA System Organ Class and Preferred Term – by Treatment Group and Dose	Phase 1 FAS Population		
3.2.25.2	Summary of Treatment-Emergent Immune-Related Adverse Events (Investigator Identified) by MedDRA System Organ Class and Preferred Term – by Treatment Group and Tumor Type	Phase 2 FAS Population		
3.2.26.1	Summary of Treatment-Emergent Immune-Related Adverse Events (Investigator Identified) by MedDRA System Organ Class, Preferred Term, and Maximum Severity – by Treatment Group and Dose	Phase 1 FAS Population		
3.2.26.2	Summary of Treatment-Emergent Immune-Related Adverse Events (Investigator Identified) by MedDRA System Organ Class, Preferred Term, and Maximum Severity – by Treatment Group and Tumor Type	Phase 2 FAS Population		
3.2.27.1	Summary of Grade 3 or Higher Treatment-Emergent Immune-Related Adverse Events (Investigator Identified) by MedDRA System Organ Class and Preferred Term – by Treatment Group and Dose	Phase 1 FAS Population		X
3.2.27.2	Summary of Grade 3 or Higher Treatment-Emergent Immune-Related Adverse Events (Investigator Identified) by MedDRA System Organ Class and Preferred Term – by Treatment Group and Tumor Type	Phase 2 FAS Population		X
3.2.28	Life Table Estimate of Time to First Grade 3 or Higher Treatment-Emergent Adverse Event – by Treatment Group and Tumor Type	Phase 2 FAS Population	X	
3.2.29.1	Summary of Adverse Events With a Fatal Outcome by System Organ Class and Preferred Term – by Treatment Group and Dose	Phase 1 FAS Population	X	
3.2.29.2	Summary of Adverse Events With a Fatal Outcome by System Organ Class and Preferred Term – by Treatment Group and Tumor Type	Phase 2 FAS Population	X	

Table No.	Title	Population	Standard	In-Text
3.2.30.1	Summary of Infusion Reactions – by Treatment Group and Dose	Phase 1 FAS Population		
3.2.30.2	Summary of Infusion Reactions – by Treatment Group and Tumor Type	Phase 2 FAS Population		

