5.2. Treatment Groups

This is a Phase 1/2, open-label, nonrandomized, multicenter, dose-escalation study. The starting dose of INCAGN01949 is 70 mg, and up to 4 doses will be tested. Data will be summarized overall and by treatment group. Treatment group is defined as the dose regimen and dose schedule initially assigned.

Dose escalation of the triplet immune therapy combinations will begin enrolling once all of the applicable doublet combinations have cleared 3 INCAGN01949 dose levels (see [Table 1](#)) or the MTD or PAD of INCAGN01949 has been determined (whichever occurs first). The starting dose of INCAGN01949 will be 2 dose levels below the last dose cohort deemed safe in the doublet combination. The triplet immune therapy combinations will be explored in parallel.

- Treatment Group A
 - INCAGN01949 + 240 mg Q2W nivolumab
- Treatment Group B
 - INCAGN01949 + 1 mg/kg Q6W ipilimumab
- Treatment Group C
 - Run-in with INCAGN01949 × 2 doses followed by INCAGN01949 + 240 mg Q2W nivolumab
- Treatment Group D
 - INCAGN01949 + 3 mg/kg Q2W nivolumab + 1 mg/kg Q6W ipilimumab
- Treatment Group E
 - Run-in with INCAGN01949 × 2 doses followed by INCAGN01949 + 3 mg/kg Q2W nivolumab + 1 mg/kg Q6W ipilimumab

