5.3. Analysis Populations

5.3.1. Full Analysis Set

The FAS includes all subjects enrolled in the study who received at least 1 dose of INCAGN01949, nivolumab, or ipilimumab. The nivolumab FAS population includes all subjects in the FAS population who received at least 1 dose of nivolumab administered in mg or mg/kg. The ipilimumab FAS population includes all subjects in the FAS population who received at least 1 dose of ipilimumab.

Table summaries, unless otherwise indicated, will be provided by treatment group and tumor type-specific cohorts.

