8.2.4. Adverse Event Summaries

An overall summary of AEs by treatment group and by tumor type as applicable will include the following:

- Number (%) of subjects reporting any TEAEs
- Number (%) of subjects reporting any DLTs
- Number (%) of subjects reporting any SAEs
- Number (%) of subjects reporting any Grade 3 or higher TEAEs
- Number (%) of subjects reporting any TEAEs related to INCAGN01949
- Number (%) of subjects reporting any TEAEs related to nivolumab
- Number (%) of subjects reporting any TEAEs related to ipilimumab
- Number (%) of subjects who temporarily interrupted INCAGN01949 because of TEAEs
- Number (%) of subjects who temporarily interrupted nivolumab because of TEAEs
- Number (%) of subjects who temporarily interrupted ipilimumab because of TEAEs
- Number (%) of subjects who permanently discontinued INCAGN01949 because of TEAEs
- Number (%) of subjects with INCAGN01949 dose reductions because of TEAEs
- Number (%) of subjects who had a fatal TEAE
- Number (%) of subjects who withdrew from study because of an TEAE

The following summaries will be produced by MedDRA term:

- Summary of TEAEs by SOC and PT
- Summary of TEAEs by PT in decreasing order of frequency
- Summary of TEAEs by SOC, PT, and maximum severity
- Summary of Grade 3 or higher TEAEs by SOC and PT
- Summary of INCAGN01949 treatment-related AEs by SOC and PT
- Summary of nivolumab treatment-related AEs by SOC and PT
- Summary of ipilimumab treatment-related AEs by SOC and PT
- Summary of Grade 3 or higher INCAGN01949 treatment-related AEs by PT in descending order of frequency
- Summary of Grade 3 or higher nivolumab treatment-related AEs by PT in descending order of frequency

- Summary of Grade 3 or higher ipilimumab treatment-related AEs by PT in descending order of frequency
- Summary of treatment-emergent SAEs by SOC and PT
- Summary of treatment-emergent SAEs by PT in descending order of frequency
- Summary of treatment-emergent non-SAE by SOC and PT.
- Summary of treatment-related SAEs by SOC and PT
- Summary of TEAEs leading to INCAGN01949 dose reduction by SOC and PT
- Summary of TEAEs leading to INCAGN01949 dose interruption by SOC and PT
- Summary of TEAEs leading to nivolumab dose interruption by SOC and PT
- Summary of TEAEs leading to ipilimumab dose interruption by SOC and PT
- Summary of TEAEs leading to discontinuation of INCAGN01949 by SOC and PT
- Summary of TEAEs leading to death by SOC and PT

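### The Phase 1 nivolumab and ipilimumab interruption tables use the whole FAS, so an overall column counts subjects never assigned the agent as event-free

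*SAP*

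**What the plan says.** SAP 5.3.1 sets up three nested populations. The broadest is the FAS: "The FAS includes all subjects enrolled in the study who received at least 1 dose of INCAGN01949, nivolumab, or ipilimumab". Inside it, "The nivolumab FAS population includes all subjects in the FAS population who received at least 1 dose of nivolumab administered in mg or mg/kg", and likewise "The ipilimumab FAS population includes all subjects in the FAS population who received at least 1 dose of ipilimumab".

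Appendix A applies the two agent-specific sets to almost every Phase 1 table about a partner drug:

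- exposure: 3.1.2.1, 3.1.3.1, 3.1.5.1 and 3.1.6.1;
- agent-related AEs: 3.2.8.1 ("Summary of Any Nivolumab Treatment-Related Adverse Events by MedDRA System Organ Class and Preferred Term"), 3.2.9.1, 3.2.11.1 and 3.2.12.1;
- agent-related fatal AEs: 3.2.14.1 and 3.2.15.1.

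Two detailed AE tables depart from this. Table 3.2.22.1 ("Summary of Treatment-Emergent Adverse Events Leading to Nivolumab Dose Interruption by MedDRA System Organ Class and Preferred Term") and Table 3.2.23.1 ("Summary of Treatment-Emergent Adverse Events Leading to Ipilimumab Dose Interruption by MedDRA System Organ Class and Preferred Term") carry the Phase 1 FAS label. So does the overall AE summary, Table 3.2.1.1. Its contents are listed in SAP 8.2.4 and include agent-specific rows such as "Number (%) of subjects who temporarily interrupted nivolumab because of TEAEs".

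SAP 5.2 lists the regimens. Group B has no nivolumab, and Groups A and C have no ipilimumab. The same section states the general display rule: "Data will be summarized overall and by treatment group".

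**The concern.** A subject who is never assigned a drug cannot interrupt it. Under the FAS label such a subject still sits in the denominator as event-free. Any pooled percentage is then lower than the rate among people who received the drug, and the never-assigned groups show 0% by construction.

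Safety and tolerability is the Phase 1 primary objective, and Protocol Section 9 says that only Phase 1 analyses will be done, so these tables remain in use. Interruption also matters more than usual for the partner drugs. The lists in SAP 8.2.4 include permanent discontinuation and dose reduction for INCAGN01949 only, which leaves interruption as the one agent-specific action-taken summary for nivolumab and ipilimumab.

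The denominators can also create an artificial ranking. Protocol 5.4.6 says that when an interruption is needed, all study treatments should be interrupted. Rates among recipients should therefore be broadly similar across the three drugs, apart from run-in and dosing-interval timing. On a common FAS denominator, the overall figures would fall from INCAGN01949 to nivolumab to ipilimumab simply because fewer subjects are assigned each drug.

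**Working it through.** **Inputs.** SAP 3.4.1 gives up to 9 subjects per dose level, 4 dose levels and 3 groups (A, B, D), with a minimum of 3 per cohort. SAP 3.4.2 gives 6 subjects per tolerated dose level in Group C and, by the same rule, in Group E. Regimens are from SAP 5.2.

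**Reproducing the plan's figure.** 9 × 4 × 3 = 108, which matches SAP 3.4.1. That is 36 per Part 1 group at the maximum and 3 × 4 = 12 at the minimum. If all four dose levels open in Part 2, Groups C and E have 6 × 4 = 24 each.

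**Formula.** Overall rate on the FAS = rate among recipients × F, where F = subjects in groups assigned the agent ÷ all Phase 1 FAS subjects. Nivolumab goes to A, C, D and E; ipilimumab goes to B, D and E.

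| Scenario | Total | Nivolumab F | Ipilimumab F |
|---|---|---|---|
| All five groups, 9 per Part 1 cohort | 36×3 + 24×2 = 156 | 120/156 = 0.77 | 96/156 = 0.62 |
| All five groups, 3 per Part 1 cohort | 12×3 + 24×2 = 84 | 72/84 = 0.86 | 48/84 = 0.57 |
| Part 1 only (A, B, D) | 108 | 72/108 = 0.67 | 72/108 = 0.67 |

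The Protocol's six-dose-level plan gives the same ratios: 180/234 and 108/126 for nivolumab, 144/234 and 72/126 for ipilimumab.

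**Illustration.** Assume that 20% of recipients interrupt each drug; the documents give no rate, and F does not depend on it. In the first row the overall column would show 20% for INCAGN01949, 0.20 × 0.769 = 15.4% for nivolumab and 0.20 × 0.615 = 12.3% for ipilimumab. In the second row the partner-drug figures are 17.1% and 11.4%; with Part 1 only, both are 13.3%. On the agent-specific FAS, F = 1 and each stays at 20%.

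**Actual enrollment.** Protocol Section 9 reports 52 subjects, all in Phase 1, with no split by group. With k subjects in groups never assigned the agent, F = (52 − k)/52. For illustration only: k = 6 gives 0.885, k = 12 gives 0.769 and k = 24 gives 0.538.

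**Agreement between tables.**

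| Quantity | Table 3.2.1.1 | Detailed table | Agree in an overall column? |
|---|---|---|---|
| Nivolumab-related TEAEs | Phase 1 FAS | 3.2.8.1, Nivolumab FAS | No |
| Ipilimumab-related TEAEs | Phase 1 FAS | 3.2.9.1, Ipilimumab FAS | No |
| Nivolumab interruption | Phase 1 FAS | 3.2.22.1, Phase 1 FAS | Yes |
| Ipilimumab interruption | Phase 1 FAS | 3.2.23.1, Phase 1 FAS | Yes |

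At the SAP maximum, for example, 24 subjects with a nivolumab-related TEAE would be 24/156 = 15.4% in one table and 24/120 = 20.0% in the other. Tables 3.2.1.1, 3.2.8.1 and 3.2.9.1 are all marked for in-text use.

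**The case against.** The strongest defense is that the FAS is the stated safety population (Protocol 9.1, SAP 8.2.1), that SAP 5.3.1 does not require the agent-specific sets for AE tables, and that each table names its population. A percentage of all treated subjects is then a legitimate, labeled descriptive figure. That stands as far as it goes. It does not explain why the interruption tables depart from the convention used for every other detailed partner-drug table.

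The overall column is also an inference. The two tables are titled by treatment group and dose, SAP 5.3.1 describes default summaries without mentioning an overall column, and the shells for nonstandard tables are in a separate document. The basis for it is the general rule in SAP 5.2, so the dilution depends on that rule being applied here.

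Four stronger readings might be inferred, and the documents do not support them:

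- *The group columns are diluted too.* Columns for groups that receive the agent are unaffected by subjects in other groups.
- *Interruption percentages contradict each other across tables.* Table 3.2.1.1 and the two interruption tables currently share the FAS. The mismatch is confined to agent-related TEAEs.
- *The ipilimumab rate could shrink to about a third.* A factor of 16/52 = 0.31 needs 36 of the 52 subjects in Groups A and C. That split is assumed, and the factor lies well below the plan-based range.
- *Dose finding is affected.* Escalation rests on DLTs (Protocol 5.4.2), and the Part 2 enrollment pause rests on severe INCAGN01949-related AEs within a group (Protocol 4.1.2). Neither uses these tables, and neither interruption table is marked for in-text use.

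It is also fair that the INCAGN01949 interruption table (3.2.21.1) has an appropriate FAS denominator and, given Protocol 5.4.6, captures much of the combination's tolerability. A careful reader would also recognize a zero in a group not assigned the drug.

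**Conclusion.** The concern holds as a minor reporting-denominator inconsistency. Tables 3.2.22.1 and 3.2.23.1 carry a population label that does not fit the SAP's own agent-specific convention. In an overall column they would understate the interruption rate among recipients by a factor of about 0.77 to 0.86 for nivolumab and 0.57 to 0.62 for ipilimumab with all five groups open, or 0.67 for both with Part 1 only. A second, separate inconsistency is that agent-related TEAEs would have different overall percentages in Table 3.2.1.1 and in Tables 3.2.8.1 and 3.2.9.1.

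These sizes assume that the overall column in SAP 5.2 is produced, that groups fill in the planned proportions, and that every subject in a run-in group goes on to receive the partner drugs. For the 52 subjects enrolled, the factor cannot be computed without the split by group. Type I error and power are not touched. The Phase 2 counterparts have the same form, but Phase 2 will not open.

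**What to change.** Make three changes together:

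1. Assign Table 3.2.22.1 to the Phase 1 Nivolumab FAS.
2. Assign Table 3.2.23.1 to the Phase 1 Ipilimumab FAS.
3. In Table 3.2.1.1, use the agent-specific N for the nivolumab and ipilimumab rows (related TEAEs and interruptions), and print not applicable for groups not assigned the agent.

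The third change is needed because relabeling the two interruption tables alone would make them disagree with Table 3.2.1.1, which they now match. It also removes the existing mismatch for agent-related TEAEs.

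The cost is two population labels and a row-level denominator in one table, with no new data or derivations, since both populations are already defined. The introduction to Appendix A treats the table list and shells as guidance and allows changes that leave the nature of the analysis intact without an SAP amendment, so this could be handled there.
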